In the most recent Phase 3 study the most commonly reported TEAEs (reported by  $\geq 2\%$  of patients) were upper respiratory tract infection (3.6%), rosacea (3.2%), application site dermatitis (3.0%), nasopharyngitis (3.0%), hypertension (2.5%), headache (2.3%), sinusitis (2.3%), application site pain (2.0%), and application site pruritus (2.0%). A majority of TEAEs were considered to be of mild or moderate severity; severe TEAEs reported by 2 or more patients included application site dermatitis (0.7%, 3/440) and application site erythema, basal cell carcinoma, and rosacea (0.5%, 2/440 each). Treatment-related TEAEs were reported during the entire study period by 8.2% (36/440) of patients. The most commonly reported treatment-related TEAEs (reported by  $\geq 1\%$  of patients) were application site dermatitis (1.8%), application site paresthesia (1.6%), application site pain (1.1%), and application site pruritus (1.1%). A majority of treatment-related TEAEs were considered to be of mild or moderate severity. Severe treatment-related TEAEs included application site erythema, and photosensitivity reaction (0.2%, 1/440) each).

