#### 8.2 Determination of Sample Size

Sample size for this study was calculated using estimated incidence rate of treatment-related AEs for daily application of oxymetazoline HCl cream 1% in conjunction with energy-based therapy. A conservative estimate of the empirical incidence rate of study drug related adverse events ( $p_0$ ) was 8.2% (based on the oxymetazoline arm of 3 Allergan pivotal studies). In the scenario of improved overall efficacy outcomes resulting from the combination of oxymetazoline treatment with energy-based devices, a 14% increase (less than 15%) in the treatment-related adverse event rate may still be tolerable or warrant further clinical development. Thus, we choose to use  $\delta = 0.14$  as the margin of indifference.

Sample size calculation for this study is based on one proportion equivalence test for testing (2-sided) the null hypothesis  $H_0$ :  $|p - p_0| > \delta$  against the alternative hypothesis  $H_1$ :  $|p - p_0| < \delta$ . A sample size of N = 43 is required for attaining a power of 80% while controlling Type-I error rate of the test at 5%. To allow for a small percentage of potential subject withdrawal, approximately 45 subjects will be enrolled into this study.

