1.1 Primary Study Objectives and Design

1.1.1 Study Design

This is a multicenter, interventional, single-arm, open-label safety and tolerability study.

Sample size calculation and power consideration are discussed in Section 8.2 of the study protocol. A total of 45 subjects with rosacea-associated moderate to severe persistent facial erythema will be enrolled into this study. Subjects will be screened for eligibility, and will be consented for the study entry.

On Day 1, all subjects will receive one of the following energy-based therapies: Potassium Titanyl Phosphate (KTP), Pulsed Dye Laser (PDL) or Intense Pulsed Light (IPL). After a 2-day washout, oxymetazoline HCl cream 1.0% will be applied once-daily starting from Day 3 up through Day 27. On Day 29, all subjects will receive a second energy-based therapy, followed by a 2-day washout and then once daily application of oxymetazoline HCl cream 1.0% up through Day 56.

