6.2 Adverse Events

Adverse events will be coded using MedDRA version 20.1 or later to give a PT and a SOC term for each event.

An adverse event (AE) is defined as any untoward medical occurrence in a clinical investigational patient administered a pharmaceutical (investigational) product and which does not necessarily have to have a causal relationship with this treatment.

All AEs will be included in by-subject AE listings. A separate listing will be created with all the distinct levels of SOC and PT, and the verbatim investigator description reported in the study. Sorting will be by earliest observed SOC, PT within SOC and then verbatim description.

A treatment-emergent adverse event (TEAE) is a post-baseline AE where (i) there is no pretreatment AE of the same MedDRA primary SOC and PT; or (ii) the maximum severity during the post-baseline period is greater than the maximal severity of any pre-treatment AE of the same MedDRA primary SOC and PT during the screening/baseline period. Note that the post-baseline period of the study starts upon the initiation of the energy-based therapy at Day 1.

Any AEs reported after signing of the Informed Consent Form and prior to the energy-based therapy on Day 1 are considered pretreatment AEs (PTAEs)

Relationship to study drug is categorized as 'related', 'possibly related', 'unlikely related', 'not related', and 'not assessable'. Relationship to trial medication as per investigator is not expected to be missing after data cleaning. However, if relationship is confirmed as missing, the AE will be considered as treatment related as per PI.

An overall summary of frequency count and the binomial incidence proportion with associated 95% CIs will be presented to describe the incidents of TEAEs. Note that 95% CIs of the binomial incidence proportion will be presented for the overall summary analyses of TEAEs, but not for the by-visit/timepoint analyses. Percentages and corresponding 95% CIs will be displayed to 1 decimal place.

Each type of AE will be tabulated by SOC and PT within SOC. The SOC and PT within SOC will be sorted by descending frequency. If a subject has multiple occurrences (start and stop) of an event associated with a specific SOC and PT, a patient will only be counted once in the incidence count for the SOC level and once at each PT within the SOC level.

The incidence of all TEAEs by SOC and PT will be presented for the following categories:

• Any TEAE

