• Any TEAE related to energy-based therapy and leading to discontinuation of study medication

• Any TEAE related to treatment (i.e., study medication or energy-based therapy or both)

- Any TEAE by maximum severity
- Any PTAE

The following listings will be provided:

- Listing of all TEAE
- Listing of patients with TEAEs related to energy-based therapy and leading to discontinuation of study medication
- Listing of patients with TEAEs leading to discontinuation of treatment

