6.3 Serious Adverse Events

A serious adverse event (SAE) is any AE occurring at any dose that results in any of the following outcomes: death, a life-threatening AE, inpatient hospitalization or prolongation of existing hospitalization, a persistent or significant disability/incapacity, or a congenital anomaly/birth defect. Important medical events that may not result in death, be life-threatening, or require hospitalization may be considered a SAE when, based upon appropriate medical judgment, they may jeopardize the patient and may require medical or surgical intervention to prevent one of the outcomes listed in this definition. Allergan considers all cancer AEs as SAEs. In addition, an abortion (spontaneous or non-spontaneous) is also considered a SAE. Any pre-planned surgery or procedure should be clearly documented in the source documents at the center by the medically qualified investigator at the time of the patient's entry into the study. If it has not been documented at the time of the patient's entry into the study, then it should be documented as a SAE and reported to Allergan.

If an unexpected AE is serious and suspected, it is a suspected "unexpected" serious adverse reactions (SUSAR). See Section of 7.1.2.1.2 of the Protocol for details, such as what is considered as "unexpected".

An overall summary of frequency count and the binomial incidence proportion with the associated 95% CIs will be presented to describe the incidents of treatment emergent SAEs. Note that 95% CIs of the binomial incidence proportion will be presented for the overall summary analyses of SAE, but not for the by-visit/timepoint analyses. Percentages and corresponding 95% CIs will be displayed to 1 decimal place.

The incidence of all treatment-emergent SAEs by SOC and PT within SOC will be presented for the following categories:

- Any SAE
- Any SAE related to energy-based therapy and leading to discontinuation of study

medication

- Any SAE related to treatment (i.e., study medication or energy-based therapy or both)
- Any SAE by maximum severity
- Any SUSAR

The following listings will be provided:

- Listing of subjects who died
- Listing of subjects with treatment-emergent SAEs
- Listing of subjects with treatment-emergent SAEs related to energy-based therapy and leading to discontinuation of study medication
- Listing of patients with treatment-emergent SAEs leading to discontinuation of

treatment

• Listing of patients with any SUSAR

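### No related-event category named in SAP 6.2 or 6.3 gives the study-drug-related rate that Protocol 8.2 uses as its 8.2% reference

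*SAP*

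**What the plan says.** Protocol 8.2 introduces its reference p0 as "A conservative estimate of the empirical incidence rate of study drug related adverse events", sets it at 8.2%, and credits it to the oxymetazoline arm of three earlier studies. Protocol 4.3 gives the same figure for the 52-week cream study: "Treatment-related TEAEs were reported during the entire study period by 8.2% (36/440) of patients". The margin is 0.14.

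The same section describes the rate being sized differently, as the "estimated incidence rate of treatment-related AEs for daily application of oxymetazoline HCl cream 1% in conjunction with energy-based therapy". It justifies the margin by a possible gain in efficacy "resulting from the combination of oxymetazoline treatment with energy-based devices".

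SAP 6.2 names two related categories for TEAEs. One is "Any TEAE related to treatment (i.e., study medication or energy-based therapy or both". The other is limited to device-related events that lead to discontinuation of study medication. SAP 6.3 repeats the pair for serious events, beginning with "Any SAE related to treatment (i.e., study medication or energy-based therapy or both". SAP 6.2 also promises a general summary, "An overall summary of frequency count and the binomial incidence proportion with associated 95% CIs will be presented to describe the incidents of TEAEs", but does not list its rows.

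On the role of the sizing section, SAP 1.1.1 says only this: "Sample size calculation and power consideration are discussed in Section 8.2 of the study protocol". Neither document plans a test against 22.2%.

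**The concern.** The reference is a drug-related rate from cream studies, while the planned summary counts events related to the cream, the device or both. The merged count also starts earlier than the cream does. SAP 6.2 opens the post-baseline period at the Day 1 energy session, and Protocol 5.6.1 starts the cream on Day 3. The merged row can therefore include device events that occur before any cream has been applied, so it is not like for like with p0.

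The primary objective concerns the cream as an adjunct. If the merged rate came out high, the named tables would not show whether the cream or the device accounted for it, and that is the result for which a safety study most needs the answer.

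A second gap follows. The SAP categories need each event to be attributed to the device, but the causality scales in Protocol 7.1.2.1 and SAP 6.2 are both defined against study drug only. The scales also differ (the SAP's has a grade for events that cannot be assessed, the protocol's does not), and neither document states which grades count as related.

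**Working it through.** **Inputs.** p0 = 0.082, margin 0.14, 5% type I error, 80% power, N = 43 and about 45 enrolled (Protocol 8.2); 36/440 = 0.0818 (Protocol 4.3); exact Clopper-Pearson 95% intervals (SAP 6). The documents give no device-related rate, so values of 5%, 10% and 15% are assumed below.

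**1. The plan's own figure.** Upper limit: 0.082 + 0.14 = 0.222. Lower limit: 0.082 − 0.14 = −0.058, so only the upper side binds. The normal approximation with one-sided 5% at the upper limit gives

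n = [(1.6449·√(0.222 × 0.778) + 0.8416·√(0.082 × 0.918)) / 0.14]² = 42.67, rounded up to 43.

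This matches the protocol.

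**2. What a merged count says about the cream.** Every drug-related event is also in the merged row, so the drug-related count lies anywhere from 0 to the merged count. No device rate has to be assumed.

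- Merged 8/45 = 17.8%, exact 95% CI 8.0% to 32.1%.
- Drug-related count as low as 0/45: exact 95% CI 0% to 7.9%.
- Drug-related count as high as 8/45: 8.0% to 32.1%.

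In the other direction, a merged upper bound below 22.2% forces the drug-related upper bound below 22.2%. For example, a merged 4/45 has a 95% upper bound of 21.2%.

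**3. How far device events could move the merged rate.** The drug-related rate is held at 8.2% and the device-related rate is q (assumed). Independence gives 1 − (1 − q)(1 − 0.082); full overlap gives the larger of the two rates; no overlap gives their sum.

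| q | Independent | Full overlap | No overlap |
|---|---|---|---|
| 5% | 12.8% | 8.2% | 13.2% |
| 10% | 17.4% | 10.0% | 18.2% |
| 15% | 22.0% | 15.0% | 23.2% |

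Under independence the merged rate reaches 22.2% at q = 1 − 0.778/0.918, about 15.3%, with no excess from the cream.

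**4. If the drug-related rate were compared with 22.2%.** With an exact one-sided 5% upper bound:

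| n | Most events allowed | Upper bound at that count | Upper bound with one more | Power at 8.2% |
|---|---|---|---|---|
| 43 | 4 | 20.0% | 22.9% | 72.5% |
| 44 | 4 | 19.6% | 22.4% | 70.8% |
| 45 | 5 | 22.0% (0.2195) | 24.6% | 84.0% |

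The stated 80% at N = 43 therefore rests on the normal approximation. The interval level also matters: at n = 45 the SAP's two-sided 95% interval allows 4 events, with 69.2% power. Any comparison would need its level stated.

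**The case against.** The strongest reply is that Protocol 8.2 can be read as making p the rate for the combination. The merged row then matches p, and the cream-only figure is simply the benchmark from which a tolerable increase is measured. That reading is open on the text. It still leaves p0 without device events, so the 14-point margin would have to absorb them, and the section does not say so.

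A reader might infer that attribution to the cream is lost. The documents do not support that. Protocol 7.1.2.1 has a causal relationship to study drug documented for each event, SAP 6.2 grades it, and all events go into by-subject listings. A drug-related row can be built from data already collected. Nor is the merged category the only one named; there is the narrow device category as well.

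A reader might also infer that the trial will test the merged rate against 22.2%, or that a primary endpoint is compromised. Neither follows. No such test is planned, Protocol 8.1 describes a descriptive analysis, and the primary endpoints (TEAEs and SAEs, dermal tolerability, telangiectasia) are reported in any case. The SAE rows have no link to 22.2%.

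The protocol also separates cream and device in time, and Protocol 5.6.1 gives separation in the event of treatment-related adverse events as a reason. This helps the investigator's judgement, and it is also a reason to show that judgement in the tables. Protocol 8.1.4 does plan tables of application-site and treatment-related events, but without saying whether the latter means drug or device; the SAP's definition prevails where the two differ.

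Finally, the unlisted rows of the overall summary, or the table shells mentioned in SAP 2.1, might already contain a drug-related row, and the eCRF might already record relationship to the device. Neither was available, so the point is limited to the SAP text.

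**Conclusion.** The point holds as a reporting gap that should be fixed: no category named in SAP 6.2 or 6.3 gives the incidence of study-drug-related events, the only rate that matches the reference in Protocol 8.2. The effect runs one way. A low merged rate carries over to the cream; a high one cannot be interpreted from the named tables, as the 0-to-8 range behind a merged 8/45 shows. That range needs no assumption. The shift in the merged rate rests on assumed device rates and on how far drug and device events overlap.

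Confidence is medium, because the shells and eCRF were not seen. Separate rows would not settle causation either: with no device-only arm, attribution still rests on the investigator's judgement.

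**What to change.** 1. In SAP 6.2, and for consistency in 6.3, report three rows: related to study drug, related to energy-based therapy, and related to either. Use the Clopper-Pearson 95% intervals already planned.
2. In Protocol 8.2, state whether p is the drug-related or the combination rate, and that 8.2% is a cream-only reference. If p is the combination rate, say that the margin must also cover device events. Then state that the section served for sizing only and that the analysis is descriptive, which fits Protocol 8.1 and SAP 1.1.1. If a comparison with 22.2% is intended instead, apply an exact one-sided 5% bound to the study-drug-related rate and state its actual power at the number analysed.
3. Define and record relationship to energy-based therapy. Use one relationship scale in both documents, with a stated cut for related and a rule for events that cannot be assessed.

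The cost is a few table rows, some SAP wording and a clarification in Protocol 8.2. The drug-related row needs no new data. The device row needs a second causality judgement per event, and queries to sites if that judgement was not recorded. The SAP allows amendment up to database lock.

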6.3 Serious Adverse Events

A serious adverse event (SAE) is any AE occurring at any dose that results in any of the following outcomes: death, a life-threatening AE, inpatient hospitalization or prolongation of existing hospitalization, a persistent or significant disability/incapacity, or a congenital anomaly/birth defect. Important medical events that may not result in death, be life-threatening, or require hospitalization may be considered a SAE when, based upon appropriate medical judgment, they may jeopardize the patient and may require medical or surgical intervention to prevent one of the outcomes listed in this definition. Allergan considers all cancer AEs as SAEs. In addition, an abortion (spontaneous or non-spontaneous) is also considered a SAE. Any pre-planned surgery or procedure should be clearly documented in the source documents at the center by the medically qualified investigator at the time of the patient's entry into the study. If it has not been documented at the time of the patient's entry into the study, then it should be documented as a SAE and reported to Allergan.

If an unexpected AE is serious and suspected, it is a suspected "unexpected" serious adverse reactions (SUSAR). See Section of 7.1.2.1.2 of the Protocol for details, such as what is considered as "unexpected".

An overall summary of frequency count and the binomial incidence proportion with the associated 95% CIs will be presented to describe the incidents of treatment emergent SAEs. Note that 95% CIs of the binomial incidence proportion will be presented for the overall summary analyses of SAE, but not for the by-visit/timepoint analyses. Percentages and corresponding 95% CIs will be displayed to 1 decimal place.

The incidence of all treatment-emergent SAEs by SOC and PT within SOC will be presented for the following categories:

- Any SAE
- Any SAE related to energy-based therapy and leading to discontinuation of study

medication

- Any SAE related to treatment (i.e., study medication or energy-based therapy or both)
- Any SAE by maximum severity
- Any SUSAR

The following listings will be provided:

- Listing of subjects who died
- Listing of subjects with treatment-emergent SAEs
- Listing of subjects with treatment-emergent SAEs related to energy-based therapy and leading to discontinuation of study medication
- Listing of patients with treatment-emergent SAEs leading to discontinuation of

treatment

• Listing of patients with any SUSAR

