### 5 STUDY ENDPOINTS

### 5.1 Primary Endpoints

The primary endpoints of the study are:

- The incidence of treatment emergent adverse events (TEAEs) and serious adverse events (SAEs).
- The number and percent of subjects with at least a 1-grade worsening from baseline in the Dermal Tolerability Assessment at any timepoint over the treatment period.
- The number and percentage of subjects with at least a 1-grade worsening from baseline in the CTA at any timepoint over the treatment period.

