### 7.1.2.1.1 Serious Adverse Events

### Serious Adverse Event Definition

An SAE is any untoward medical occurrence or effect that, at any dose,

- Results in death.
- Is life-threatening (an AE is life-threatening if the subject was at immediate risk of death from the event as it occurred, ie, it does not include a reaction that might have caused death if it had occurred in a more serious form).
- Requires or prolongs inpatient hospitalization. (Complications occurring during hospitalization are AEs and are SAEs if they cause prolongation of the current hospitalization. Hospitalization for elective treatment of a pre-existing non-worsening condition is not, however, considered an AE. The details of such hospitalizations must be recorded on the medical history or physical examination page of the eCRF).
- Results in persistent or significant disability/incapacity. An AE is incapacitating or disabling if it results in a substantial and/or permanent disruption of the subject's ability to carry out normal life functions.
- Results in a congenital anomaly/birth defect.

Allergan considers all cancer AEs as SAEs. Any abortion (spontaneous or nonspontaneous) is also considered a SAE.

In addition, medical and scientific judgement is required to decide if prompt notification is required in situations other than those defined for SAEs above. This may include any event that the investigator regards as serious that did not strictly meet the criteria above but may have jeopardized the subject or required intervention to prevent one of the outcomes listed above, or that would suggest any significant hazard, contraindication, side effect, or precaution that may be associated with the use of the study drug.

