# 7.1.3 Other Assessments

# 7.1.3.1 Demographic Information and Medical History

At the screening visit, subject demographic data will be collected. These data include date of birth, age, gender, race, and ethnicity. A medical history will also be obtained from each subject at this visit. Medical history includes a detailed history of prior cosmetic and surgical procedures, with start and stop dates, if applicable, as well as any discontinuations due to intolerability or toxicity.

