The purpose of this statistical analysis plan (SAP) is to provide details of the statistical analyses and reporting that are outlined in the study protocol, which is dated on Oct 12, 2017 and titled "Multicenter, Open-Label, Interventional Study on the Safety and Tolerability of Oxymetazoline and Energy-Based Therapy in Subjects with Rosacea". This SAP should be reviewed in conjunction with the study protocol. Information contained in the protocol will not be restated unless it is essential for the descriptions in this SAP. In case of any discrepancies (for example, the definition of the Safety Analysis Population) between the protocol and the SAP, the SAP will supersede the protocol, as the SAP is intended to be more specific and precise with respect to statistical analysis and reporting. Any amendments to the SAP will be made prior to database lock. Any additional analyses not described in the final SAP or deviations from the final SAP will be documented in the clinical study report.

This study is a Phase 4 study sponsored by Allergan Plc. This study is a multicenter, interventional, open-label safety and tolerability study to evaluate the safety and tolerability of oxymetazoline HCl cream 1.0% when used as an adjunctive treatment to energy-based therapy for subjects with moderate to severe persistent facial erythema associated with rosacea.

Approximately 45 subjects will be enrolled into this study at 4 clinical sites in the United States. The duration of the study for each subject is 10 weeks. This includes a screening period of up to 2 weeks, a treatment period of 8 weeks, comprising of daily dosing of study drug and 2 energy-based therapy sessions, followed by a final exit visit at Week 8 (Day 56).

There will be no interim analysis. One final analysis is planned for this study. The final analysis will be performed at the completion of the study. Database lock will be executed for the final analysis.

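### SAP 6.3 makes a pre-planned procedure not documented at entry an SAE, which conflicts with Protocol 7.1.2.1.1 and with the SAP's own definitions, so SAE incidence in the first primary endpoint has two definitions

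*SAP*

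**What the plan says.** Protocol 5.1 makes the incidence of TEAEs and SAEs the first primary endpoint. SAP 6.3 reports treatment-emergent SAEs as a count and a binomial proportion with a 95% CI, and SAP section 6 names the Clopper-Pearson exact method.

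The two documents then treat planned procedures differently:

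- **Protocol 7.1.2.1.1 (SAE definition):** "Hospitalization for elective treatment of a pre-existing non-worsening condition is not, however, considered an AE". On recording: "The details of such hospitalizations must be recorded on the medical history or physical examination page of the eCRF". The exemption does not depend on when the record was made.
- **SAP 6.3:** "Any pre-planned surgery or procedure should be clearly documented in the source documents at the center by the medically qualified investigator", at the time of study entry. If that was not done, "then it should be documented as a SAE and reported to Allergan".

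SAP 6.3 itself opens with a narrower rule: "A serious adverse event (SAE) is any AE occurring at any dose that results in any of the following outcomes". SAP 6.2 defines an AE as an untoward occurrence. On conflicts between the documents, the SAP introduction says "the SAP will supersede the protocol, as the SAP is intended to be more specific and precise with respect to statistical analysis and reporting". SAP section 11, which lists deviations from the protocol, names only changes to the analysis populations.

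**The concern.** Take an elective admission planned before consent, for a stable condition, that nobody wrote down at entry. Under the protocol it is not an AE and so cannot be an SAE. Under the last sentence on this subject in SAP 6.3 it is an SAE. Only the date of a source note separates the two readings.

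An outpatient procedure is a second case. The protocol exemption is worded for hospital stays and does not mention it, but the procedure meets none of the protocol's listed outcomes. It could become serious there only through the medical-judgement paragraph. The SAP sentence makes it an SAE without any such judgement.

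The study is small, open-label and single-arm, so there is no control rate to set one case against. A single reclassified procedure would turn a report of no SAEs into a report of one. If performed after the Day 1 energy-based session, it would normally count as a TEAE as well.

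**Working it through.** **Setting the rules side by side**

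| Event after Day 1, planned before entry, not documented at entry | Protocol 7.1.2.1.1 | SAP 6.3, opening definition with 6.2 | SAP 6.3, pre-planned-procedure sentences |
|---|---|---|---|
| Elective hospital stay, pre-existing condition, not worsening | Not an AE | Has a listed outcome, but must first be untoward | SAE |
| Outpatient procedure, uneventful | No listed outcome met | No listed outcome met | SAE |

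The last column differs from the protocol in both rows. In the second row it also contradicts the SAP's own opening definition. In the first row it drops the requirement that the event be an AE at all.

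**Can a site that follows the protocol miss the SAP's condition?** Protocol 7.1.3.1 says "Medical history includes a detailed history of prior cosmetic and surgical procedures", which looks backwards and does not explicitly ask for procedures still to come. The medical history page is nevertheless filled in only at Screening and Day 1 (Table 1; sections 6.1.1 and 6.1.2), so that recording route is in practice documentation at entry. The physical examination is done at Screening and at exit, so its exit page is the one later route. A site can therefore follow the protocol and still fail the SAP's condition, but only by that route.

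**Effect on the reported figure**

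The documents give no expected SAE rate, so there is no planned SAE figure to reproduce. The denominator comes from Protocol 8.2, which requires N = 43 and enrols about 45. That N can be reproduced with p0 = 0.082, an upper limit of 0.082 + 0.14 = 0.222, a one-sided 5% level and 80% power:

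n = [(1.645 × √(0.222 × 0.778) + 0.842 × √(0.082 × 0.918)) / 0.14]² = 42.67, rounded up to 43.

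For x events in n subjects, the Clopper-Pearson limits are Beta(0.025; x, n − x + 1) and Beta(0.975; x + 1, n − x). With x = 0 the lower limit is 0 and the upper limit is 1 − 0.025^(1/n). Assuming no other SAE:

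| Reclassified procedures | n = 43 | n = 45 |
|---|---|---|
| 0 | 0.0% (0 to 8.2%) | 0.0% (0 to 7.9%) |
| 1 | 2.3% (0.1 to 12.3%) | 2.2% (0.1 to 11.8%) |
| 2 | 4.7% (0.6 to 15.8%) | 4.4% (0.5 to 15.1%) |

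The counts of one and two are assumptions. The treatment-related AE rate behind the sample size is touched only if the event is judged related, or if its relationship is confirmed missing and so defaults to related under SAP 6.2.

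**The case against.** The strongest reply is that the SAP sentences may never act on the data. They read as instructions to investigators, not as a derivation rule, and nothing in the SAP programs a procedure into an SAE. Sites classify seriousness and report SAEs under the protocol, and procedures have their own record under concurrent procedures. The SAP's precedence clause concerns statistical analysis and reporting, not how sites fill in the eCRF. This stands. It means that a wrong count is possible, not that one will occur.

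Other points also stand in part. A single case would be visible, because SAP 6.3 provides tables by SOC and PT, a treatment-related category and subject listings. No test compares SAE incidence with a threshold. The SAP rule errs towards over-reporting, and it gives some check that a procedure really was planned before entry. The fix should keep that check visible.

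A reader might infer more than the documents support:

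- **That the protocol exempts all elective treatment.** It exempts hospital stays for elective treatment of a pre-existing condition that is not worsening. Outpatient procedures fall outside because they meet no listed outcome, not because an exemption names them.
- **That the protocol leaves documentation at entry entirely open.** The medical history route closes at Day 1.
- **That a false SAE is likely.** To be counted, a procedure must be planned before entry, missed at entry, performed after the Day 1 session within about 8 weeks, and then entered as an SAE. The documents give no rate for this. With an assumed rate r per subject, the chance of at least one in 43 is 1 − (1 − r)^43, which is about 4% at r = 0.1% and 89% at r = 5%. A range that wide shows only that the probability cannot be stated.

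**Conclusion.** The conflict is real. For the same event the protocol and SAP 6.3 give different answers, SAP 6.3 disagrees with its own opening definition, the SAP claims precedence, and section 11 does not declare the difference. SAE incidence, part of the first primary endpoint, therefore has two conflicting definitions.

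The practical size is limited. Each affected subject adds 1/43 = 2.3 percentage points (1/45 = 2.2), and the first one raises the upper 95% limit from 8.2% to 12.3% at n = 43. This assumes no other SAE and that the SAP sentence is applied to the data. The number of such subjects is unknown and probably low. It would be too strong to conclude that the primary result will depend on paperwork, since the documents do not show that the SAP sentence governs what sites record. The point is worth correcting because the endpoint is primary and the correction is cheap.

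**What to change.** Before database lock, amend SAP 6.3:

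1. Delete the two sentences on pre-planned surgery and procedures.
2. State that an event counts as an SAE only if it is an AE that meets Protocol 7.1.2.1.1, including the elective-hospitalization exemption as worded there and the medical-judgement paragraph. Do not write a wider exemption for all elective treatment.
3. List pre-planned procedures with a flag for whether each was documented at entry, and do not count them as SAEs on that ground alone. The flag lets a reader see any procedure whose planning before entry was not recorded.
4. If the sponsor does intend the stricter rule, reconcile the two passages so that sites and analysts work from one definition, and declare the difference in SAP section 11.

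The cost is one SAP wording change and one listing. The SAE definition needs no new data, and the sample size does not change. The flag can be filled only from what the source documents and eCRF already show.
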